12.4.3 Handling of remaining intercurrent events of primary endpoint

For the primary analysis, only CR assessments after first dose of study treatment and prior start of any other anti-neoplastic therapy or HSCT are considered. An adequate response assessment is considered any disease assessment indicating response status apart from "unknown" or "not done".

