2.5.1.2 Cohort 2 of Safety run-in (Part 1) and Expansion (Part 2)

The primary endpoint is the proportion of participants included in the FAS and assigned to sabatolimab at the 800 mg Q4W dose level (in both safety run-in and expansion parts) who achieved a complete remission (CR) as per investigator assessment.

Response assessment rules

Response assessment will be performed by the investigator according to the assessment schedule depicted in protocol Table 8-1 based on available bone marrow assessment (C3D1, C7D1, C10D1, C13D1 and then C19D1, C25D1 and then every 12 cycles), hematology data (at D1, D8, D22 of the first 2 cycles and then D1 and D8 of each cycle until end of treatment and then every 12 weeks) and all transfusions records as detailed in s using the modified version of the published response criteria IWG for MDS. Moreover, response assessments can be performed at any time if clinically indicated, e.g. for confirmation of response but also for any suspicion of progression/relapse. These assessments are recorded as an unscheduled visit in the eCRFs and will be considered for the overall determination of response and progression/relapse with the respective assessment date.

The investigator does not determine best overall response, he/she is assessing only the response based on the given bone marrow and peripheral blood data, the history of transfusions and myeloid growth factor received within the last 2 weeks.

The best overall response (BOR) will be derived based on the CR primary endpoint rules by Novartis as below:

- CR = at least one determination of CR without progression or relapse from CR within the four weeks after CR
- mCR = at least one determination of mCR (and not qualifying for a CR).
- PR = at least one determination of PR (and not qualifying for a CR, mCR).
- HI = at least one determination of HI (and not qualifying for a CR, mCR, PR)
- SD = at least one SD assessment and not qualifying for CR, mCR, PR or HI).
- PD = progression after start of treatment and not qualifying for CR, mCR, PR, HI or SD.
- UNK = all other cases (i.e., not qualifying for confirmed CR or mCR or PR or HI and without SD or progression).

Details for the definition of response categories (captured in the eCRF by the Investigator) as defined in Table 8-2 of the protocol, are described in Table 2-2 below.

Response category	Definition [#]	
Complete remission (CR)	Bone marrow:	

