*Pretreatment counts correspond to the baseline (not influenced by transfusions)

**Definition of transfusion dependence and independence for red blood cells (RBC) and/or platelets are described below.

***maximum remission/response levels correspond to the best values reported in post baseline.

Transfusions Status Definitions for RBC/platelets

Transfusions for intercurrent diseases not due to study indication (e.g. bleeding, surgical procedure, hemolysis, infections) should not be taken into account for the following:

Transfusion dependence:

1. At baseline: participants having received ≥ 3 units of transfusion within the 8 consecutiveweekspriorto2. Post-baseline: participants having received ≥ 3 units of transfusion within any 8consecutive weeks during the course of the study

Transfusion independence:

1. At baseline: participants having received 0 units of transfusion within the 8 consecutive weeks prior to baseline.

2. Post-baseline: participants having received 0 units of transfusion within any 8 consecutive weeks during the course of the study.

Primary estimand

The primary clinical question of interest is the following:

Is sabatolimab 800 mg Q4W in combination with fixed doses of azacitidine (75 mg/m² Day 1-7) and venetoclax (400 mg Day 1-14) associated with improved efficacy (i.e. CR rate $\geq 50\%$) for participants with high or very high risk MDS?

The primary endpoint (combining data from cohort 2 of the Safety run-in (Part 1) and the Expansion (Part 2) (i.e. sabatolimab 800 mg (Q4W)) is the proportion of participants achieving a complete remission (CR) as per investigator assessment.

The primary efficacy estimand is described by the following five attributes:

- **Population:** Adult participants as described by inclusion/exclusion criteria not eligible for intensive chemotherapy nor for HSCT with high or very high risk MDS (IPSS-R criteria) (Greenberg et al 2012) as per inclusion/exclusion criteria and as assessed locally by the investigator.
- Variable: Best overall response among all disease response assessments as assessed by investigator per modified IWG MDS criteria (Cheson et al 2006) up to new anti-cancer therapy (including HSCT).
- **Treatment:** Study treatment initiates sabatolimab 800 mg Q4W + azacitidine (75 mg/m² Day 1-7) + venetoclax (400 mg Day 1-14). Participants will continue treatment

until a reason of treatment discontinuation is met (e.g. progression, unacceptable toxicity, HSCT).

- Intercurrent events:

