 - **Study treatment modification:** all CR will be taken into account regardless of any study treatment component interruption, dose adjustment or permanent discontinuation.
 - **Concomitant medications and supportive care:** A participant may receive blood transfusion as supportive care and prophylactic treatment as clinically indicated (e.g. antiemetics, antibiotics, antifungals). All CR will be taken into account regardless of any concomitant medication administration including prohibited medications.
 - New anti-cancer therapy/HSCT: CR achieved after initiation of a new anti-cancer therapy or HSCT will not be taken into account.
- Summary measures: The CR rate and the 95% confidence interval (CI).

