2.5.3 Handling of missing values/censoring/discontinuations

2.5.3.1 Cohort 2 of Safety run-in (Part 1) and Expansion (Part 2)

For the determination of CR, only assessments after first dose of study treatment and prior to the start of any other anti-neoplastic therapy/HSCT as per investigator evaluation are considered. An adequate response assessment is considered any disease assessment indicating response status apart from "unknown" or "not done". Participants who discontinued trial prior to the first efficacy assessment (i.e. C3D1) will be reported with best response as 'Unknown'.

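### The SAP counts a CR only if no progression or relapse follows within four weeks; the protocol has no such condition, SAP Section 3 does not declare it, and the duration endpoints do not repeat it

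*SAP*

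**What the plan says.** **Where the condition stands.** In SAP 2.5.1.2 the sponsor derives best overall response (BOR) from the investigator's visit-level assessments. The first line is "CR = at least one determination of CR without progression or relapse from CR within the four weeks after CR". The next is "mCR = at least one determination of mCR (and not qualifying for a CR", followed by PR, HI, SD and PD, and the list closes with "UNK = all other cases (i.e., not qualifying for confirmed CR or mCR or PR or HI and without SD or progression". The response categories are those "captured in the eCRF by the Investigator".

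**Where it does not stand.** Protocol 12.4.1.2 and the SAP estimand define the variable in the same words: "Best overall response among all disease response assessments as assessed by investigator per modified IWG MDS criteria". The one intercurrent-event rule that removes a CR is "CR achieved after initiation of a new anti-cancer therapy or HSCT will not be taken into account". SAP 2.5.3.1 says "only assessments after first dose of study treatment and prior to the start of any other anti-neoplastic therapy/HSCT as per investigator evaluation are considered", and Protocol 12.4.3 says "only CR assessments after first dose of study treatment and prior start of any other anti-neoplastic therapy or HSCT are considered". Protocol Table 8-2 and SAP Table 2-2 do not require a CR to last, although both tables set a duration for SD (more than 8 weeks) and for HI (at least 8 weeks). SAP Section 3 lists two departures from the protocol, the dropped primary CR analysis and the dropped patient-reported outcome analysis, and nothing about BOR.

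**What is still reported.** SAP 2.5.2.2 keeps the CR rate by dose level with an exact 95% interval. SAP 2.6.1.2 builds CR+mCR and ORR on BOR. It starts duration of CR, of CR/mCR and of response at the first investigator-assessed occurrence.

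**The concern.** The CR rate is the one primary efficacy result left in the abbreviated report. A condition on how long a remission lasts changes which participants are in its numerator. If anyone fails the condition, the reported rate is no longer the protocol's rate, and a reader of SAP Section 3 would not know.

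There are two further consequences. The lower BOR lines do not say whether a failed CR that also meets the mCR marrow criterion counts as mCR, or whether relapse counts as progression. Read literally, a documented remission can therefore be reported as unknown and leave CR, CR+mCR and ORR together. Also, since the duration endpoints do not repeat the condition, one participant could be outside the CR rate and inside the analysis of duration of CR. The EFS rule on reaching CR within six cycles does not say which CR it uses.

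**Working it through.** **1. Design figures.** The plan's rule of at least 36 CRs in 70 reproduces by exact binomial tail: 0.0197 at a CR rate of 0.386 (stated 2.0%) and 0.7998 at 0.557 (stated 80%). These figures treat each participant as CR or not and do not depend on the four-week wording. No stated figure in the plan rests on it.

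**2. What the BOR list does with a failed CR.** I applied the list literally: each lower response needs its own recorded determination, and relapse is not progression. C3D1 is day 2 × 28 + 1 = 57; C7D1 is day 6 × 28 + 1 = 169. A lag of 25 days is inside four weeks.

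| Recorded assessments | BOR | CR | CR+mCR | ORR | Duration of CR |
|---|---|---|---|---|---|
| CR at C3D1, relapse 25 days later | UNK | out | out | out | in |
| CR at C3D1, progression 25 days later | PD | out | out | out | in |
| SD earlier, CR at C7D1, relapse 25 days later | SD | out | out | out | in |
| HI or PR earlier, then the same | HI or PR | out | out | in | in |
| mCR earlier, then the same | mCR | out | in | in | in |
| CR at C3D1, relapse 25 days later, CR at C7D1 that holds | CR | in | in | in | in |

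The last column assumes that duration of CR takes any investigator-assessed CR, as its text reads. If a CR record may itself serve as a determination of mCR, the first three rows become mCR wherever the marrow criterion is met. If relapse counts as progression, the first row becomes PD instead of UNK, and the participant is still out of all three rates.

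**3. When a CR also meets the mCR marrow criterion.** mCR needs blasts of at most 5% and a fall of at least 50% from baseline. The fall is (baseline − blasts at CR) / baseline. For a CR at 5% blasts:
- baseline 10%: (10 − 5)/10 = 50.0%, met;
- baseline 9%: 4/9 = 44.4%, not met;
- baseline 6%: 1/6 = 16.7%, not met (blasts of 3% or less would be needed).

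So the criterion is always met with baseline blasts of 10% or more. Below that it is met only when blasts at CR are at most half of baseline.

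**4. How an early failure could be recorded.** Scheduled response visits from C3D1 to C25D1 are 16, 12, 12, 24 and 24 weeks apart, so none falls within four weeks of another. A failure needs an unscheduled response record, which SAP 2.5.1.2 admits into the derivation. Blood counts are scheduled 7 and 28 days after C3D1 (days 64 and 85). With the ±3-day visit window the second can fall on day 82, which is 25 days after a CR on day 57. Three of the five relapse criteria are count falls that need no marrow. Each has a size threshold, and relapse applies only when there is no explanation other than MDS.

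**5. Size per case.** Planned cohort sizes are about 12 (800 mg) and about 6 (400 mg). One case with no later CR that holds moves the rate by 1/12 = 8.3 points or 1/6 = 16.7 points. The Clopper-Pearson limits are the 2.5% quantile of Beta(x, n − x + 1) and the 97.5% quantile of Beta(x + 1, n − x). With assumed counts:
- 800 mg: 6/12 = 50.0% (21.1 to 78.9) becomes 5/12 = 41.7% (15.2 to 72.3), while duration of CR still has n = 6;
- 400 mg: 3/6 = 50.0% (11.8 to 88.2) becomes 2/6 = 33.3% (4.3 to 77.7).

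**6. EFS.** Take CR on day 57 and relapse on day 82, with no later CR. If the six-cycle rule uses the investigator's CR, the event is at day 82. If it uses BOR-derived CR, the participant never reached CR and the event is placed at start of treatment.

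**The case against.** **Supplying a BOR algorithm is ordinary SAP work.** The protocol names BOR without giving a derivation. The SAP estimand's variable is BOR, which the same SAP section defines, so the condition enters through it. This stands in part. A reader might infer that the SAP flatly contradicts its own estimand; it does not. But Protocol 12.4.3 states which CRs are considered, the SAP's added line removes some of them, and Section 3 is silent.

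**Every case has a class.** A reader might infer that the SAP leaves a failed CR unclassified. The documents do not support that: the list is exhaustive and ends in a catch-all. The gap is narrower, namely the two unanswered questions on mCR and on relapse.

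**Loss from CR+mCR and ORR is only one reading.** This is correct. Nothing says that a CR record cannot also serve as an mCR determination, and several peripheral-blood criteria are the same for relapse and progression. The table in the working shows the literal reading, not a settled result.

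**The mismatch with duration is possible, not established.** The duration text neither applies nor disclaims the condition. Individual times and censoring types will be listed, and Kaplan-Meier output depends on the amount of data, so a discrepancy could be seen. That limits the harm but does not settle which CR definition applies.

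**It may never occur.** This is also fair. It needs an unscheduled response record within four weeks and a fall attributable to MDS.

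**Conclusion.** The point holds as a discrepancy between SAP and protocol that should be fixed. The SAP adds an undeclared durability condition to the CR rate, leaves two classification questions open for CRs that fail it, and does not carry the condition into the durations or the EFS six-cycle rule.

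The number of participants affected cannot be found from the documents and may be zero. The 8.3-point shift per case rests on an assumed n of 12 at 800 mg, and the intervals shown rest on assumed counts. CR+mCR falls only if no mCR is credited; ORR falls only if no mCR, PR or HI is credited.

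A reader might infer that the condition weakens the 36-of-70 success rule or its 80% power. The documents do not support that: they give no share of CRs that would fail, and the formal CR decision has been dropped (SAP 2.5.2.2 and Section 3). Only descriptive results are affected.

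**What to change.** - Report the CR rate by the protocol rule: any investigator-assessed CR after first dose and before new antineoplastic therapy or HSCT.
- If the four-week version is kept, declare it in SAP Section 3 and show it as a sensitivity analysis. In that version, count a failed CR as mCR when the mCR marrow criterion is met, and state whether relapse counts as progression, so that the class of the remaining cases is explicit.
- Use the same CR definition for the CR rate, duration of CR and the EFS six-cycle rule, and say so in each place.

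The cost is SAP wording and a small change to the BOR derivation. No new data are needed: the investigator's response categories are already captured, and SAP 2.6.1.2 already lists marrow blast percentages.

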2.5.2 Statistical hypothesis, model, and method of analysis

2.5.2.1 Safety run-in (Part 1)

DLT analysis

A Bayesian model will be used to assess whether sabatolimab at the two tested dose levels is not meeting overdose criteria when added to azacitidine and venetoclax in participants from the DDS. The relationship between dose and the probability of DLT is modeled using a logistic regression model. Detail of the characteristics of this Bayesian model is provided in Appendix Section 16.1 of the protocol.

After each cohort in the safety run-in part, the posterior distribution for the risk of DLT for new participants at the dose level of interest will be evaluated. The posterior distributions will be summarized to provide the posterior probability that the risk of DLT for each dose level of sabatolimab lies within the interval [33%, 100%] (i.e. excessive toxicity).

2.5.2.2 Cohort 2 of Safety run-in (Part 1) and Expansion (Part 2)

CR primary analysis

As Novartis decided to halt the enrollment in the expansion part, only the CR rate by the dose level of sabatolimab with exact 95% confidence interval will be reported in the abbreviated CSR.

2.5.3 Handling of missing values/censoring/discontinuations

2.5.3.1 Cohort 2 of Safety run-in (Part 1) and Expansion (Part 2)

For the determination of CR, only assessments after first dose of study treatment and prior to the start of any other anti-neoplastic therapy/HSCT as per investigator evaluation are considered. An adequate response assessment is considered any disease assessment indicating response status apart from "unknown" or "not done". Participants who discontinued trial prior to the first efficacy assessment (i.e. C3D1) will be reported with best response as 'Unknown'.

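### SAP 2.5.3.1, read literally, labels participants who leave the trial before C3D1 as best response Unknown even when an earlier assessment exists, which conflicts with the best-response derivation in SAP 2.5.1.2

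*SAP*

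**What the plan says.** SAP 2.5.3.1, on missing values and discontinuations for the 800 mg CR analysis, contains two rules. The first sets which assessments are eligible for CR: "only assessments after first dose of study treatment and prior to the start of any other anti-neoplastic therapy/HSCT as per investigator evaluation are considered". It calls an assessment adequate if it gives a response status other than unknown or not done. The second sets a default: "Participants who discontinued trial prior to the first efficacy assessment (i.e. C3D1) will be reported with best response as" Unknown.

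SAP 2.5.1.2 holds the response rules and the derivation of best overall response (BOR). On timing it says that "response assessments can be performed at any time if clinically indicated", and continues: "These assessments are recorded as an unscheduled visit in the eCRFs and will be considered for the overall determination of response and progression/relapse". Three of its BOR categories matter here:

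- For progressive disease, the rule reads: "PD = progression after start of treatment and not qualifying for CR, mCR, PR, HI or SD"
- For complete remission, it reads: "CR = at least one determination of CR without progression or relapse from CR within the four weeks after CR"
- For the residual category, it reads: "UNK = all other cases (i.e., not qualifying for confirmed CR or mCR or PR or HI and without SD or progression"

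None of the three refers to C3D1.

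SAP 2.5.1.2 also adopts the assessment schedule in protocol Table 8-1. That table places marrow and response assessments at C3D1 and later cycles, and also at EOT. Protocol Section 8 puts the EOT visit within 14 days of the decision to stop treatment.

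**The concern.** The parenthesis in 2.5.3.1 equates the first efficacy assessment with a fixed visit, C3D1, which is study Day 57 in SAP Table 4-1. Taken at its word, it turns C3D1 into a cut-off: whoever leaves the trial before it is Unknown, whatever was documented earlier. Under 2.5.1.2 the same participant could be PD, CR, mCR or PR. A documented progressor cannot be Unknown under 2.5.1.2, yet must be Unknown under the literal text of 2.5.3.1.

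Two things are at stake. One is whether an early treatment failure is shown as a failure or as missing data in the best-response categories. The other is agreement between endpoints in one report. The same person could be a PFS progression event and a best response of Unknown. An early CR could enter duration of CR and time to CR/mCR, which run from the first occurrence of response, and still be absent from the CR rate.

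**Working it through.** The plan gives no figure for this point. Its design figures do not depend on it: with success at 36 or more CRs in 70, P(X ≥ 36) is 0.0197 at a CR rate of 38.6% (stated 2.0%) and 0.8005 at 39/70 (stated 80%). The check is therefore a comparison of rules, followed by a count of what each relabelling does.

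**1. Can an assessment exist before C3D1?** Yes, in two ways. SAP 2.5.1.2 allows an unscheduled assessment at any time if clinically indicated. Protocol Table 8-1 schedules one at EOT, which falls before Day 57 for someone who stops in Cycle 1 or early Cycle 2. The list of marrow visits inside 2.5.1.2 omits EOT, but the section takes its schedule from Table 8-1. Progression can also be met on blood counts, transfusion dependence or acute leukemia (SAP Table 2-2), and hematology is drawn on D1, D8 and D22 of Cycles 1 and 2. So C3D1 is not always the first efficacy assessment.

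**2. The rules side by side**, for a participant who leaves the trial before C3D1:

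| Documented before leaving | BOR under 2.5.1.2 | BOR under 2.5.3.1, literal |
|---|---|---|
| Progression only | PD | Unknown |
| CR, no progression or relapse within four weeks | CR | Unknown |
| mCR (not CR) | mCR | Unknown |
| PR (not CR or mCR) | PR | Unknown |
| No adequate assessment | Unknown | Unknown |

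The rules agree only in the last row.

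**3. Effect on the reported rates.** The denominator is the FAS at 800 mg, and Unknown stays in it as a non-response.

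| Relabelled as Unknown | CR count | CR+mCR count | ORR count |
|---|---|---|---|
| PD | 0 | 0 | 0 |
| CR | −1 | −1 | −1 |
| mCR | 0 | −1 | −1 |
| PR | 0 | 0 | −1 |

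HI must last at least 8 weeks, so it cannot normally be established before Day 57 and does not add a case.

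**4. Size per participant.** Cohort 2 was planned at about 12. Assume n = 12 and, for illustration only, 5 CRs.

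- One PD relabelled: CR rate stays 5/12 = 41.7% (exact 95% CI 15.2 to 72.3).
- One CR relabelled: 4/12 = 33.3% (9.9 to 65.1), a drop of 1/12 = 8.3 points.

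**5. Time-to-event endpoints (SAP 2.6.1.2).** PFS takes progression, relapse or death from their dates. EFS counts stopping treatment without CR before 6 cycles as an event at start of treatment. OS counts all deaths. None of these definitions refers to BOR, so relabelling PD as Unknown alters none of them.

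**The case against.** The best defence is that the sentence is only a default for participants with no response data. It sits under the missing-values heading, follows directly on the definition of an adequate assessment, and names C3D1 because that is the first routine on-treatment visit for response. The residual definition of Unknown in 2.5.1.2 excludes progression, which suggests the same intent. The default also makes sense for a non-progressor: SD needs more than 8 weeks without progression and HI must last at least 8 weeks, so someone who leaves before Day 57 will usually qualify for neither. This may well be what was meant, but the text does not say so. The gloss names a visit rather than the absence of data, and no precedence is stated.

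A reader might infer more: that every early progressor is caught, that documented progression is erased from the report, or that the efficacy result is biased. The documents do not support this.

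- The sentence applies to those who discontinued the trial. Under protocol 9.1.1, stopping study treatment is not withdrawal unless consent is withdrawn, and such participants continue into survival follow-up (9.1.1.3). A participant who progresses at week 5 and stops treatment is not caught for that reason alone; death, consent withdrawal or loss to follow-up before C3D1 is also needed.
- The progression stays in PFS and EFS, any death stays in OS, and SAP 2.6.1.2 lists individual times and event types.
- Moving PD to Unknown changes no response rate. The 8.3 points would then be only a shift between two non-response labels.

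**Conclusion.** The conflict between the two SAP sections is real on the literal text and nothing in the documents resolves it. It is a minor point.

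For a documented early progression, only the best-response label is affected. For a documented early CR, mCR or PR followed by death, withdrawal or loss to follow-up before C3D1, one or more of the CR, CR+mCR and ORR counts falls by one, or 8.3 points per participant if n = 12. That sequence needs an early marrow response and then departure from the trial before about Day 57, so it should be uncommon. The documents do not give the number affected, and it may be zero.

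No trial decision depends on it: SAP 2.5.2.2 and Section 3 drop the formal CR analysis and leave a descriptive rate with an exact interval. The conclusion rests on the literal reading of the C3D1 parenthesis and on taking leaving the trial in the sense of protocol 9.1.1; the size rests on the assumed 12 participants.

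**What to change.** Replace the sentence in SAP 2.5.3.1 with:

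> Participants with no adequate post-baseline response assessment, scheduled (including EOT) or unscheduled, will be reported with best response as Unknown; all others follow the BOR derivation in Section 2.5.1.2.

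A participant whose early assessment meets none of the response, SD or progression categories still falls into Unknown through the residual category in 2.5.1.2, so the default is kept where it is needed. The cost is one SAP sentence, settled before database lock, and the matching line in the BOR program. It needs no new data, no protocol change and no recalculation of design figures.
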